3.1 Primary Objective

We will determine both an “intensity (difficulty) effect” and an “emotion effect” of task-induced fMRI activity in the scanner, collecting these measures in the same subjects. Participants will receive two working memory tasks:

1a) Sternberg Sorting Task (SST): a cognitive task comparing low-load vs. high-load conditions in which the picture stimuli are letters.

1b) International Affective Picture System (IAPS): an emotional task using IAPS picture that will also compare low load and high load conditions. The number of images will vary by condition load, but for both the high-load & low-load conditions, participants will look at IAPS pictures and answer questions about the images. Further, jittered within this design will be both neutral and negative blocks of IAPS pictures.

We will compare low-load vs. high-load brain activation and connectivity in the cognitive vs. emotional tasks.

Hypothesis 1a: Compared with the maintenance (low-load) SST condition, the high-load cognitive SST condition will produce greater DLPFC activation and dIPFC/sgACC anticorrelation.

Hypothesis 1b: Compared with the low-load IAPS emotional task, the high-load IAPS emotional pictures will produce higher activity in the DLPFC and dIPFC/sgACC anticorrelation.

Hypothesis 1c: The picture rating for arousal will be correlated with the activity in the DLPFC and dIPFC/sgACC anticorrelation.

Secondary Objectives:

Aim 2: to determine which task provides greater augmentation of the TMS-induced DLPFC activation, participants will receive in randomized order:

- 1) The cognitive SST working memory task or the IAPS task alone
- 2) rTMS + the cognitive SST working memory task or rTMS + the IAPS emotional task in randomized order. rTMS and the cognitive tasks will be conducted in the fMRI scanner where brain activation to a TMS probe and connectivity will be obtained.
- 3) rTMS alone

Hypothesis 2a: rTMS + either task will have greater DLPFC activation and greater dIPFC/sgACC anticorrelation than rTMS alone.

Hypothesis 2b: rTMS + the IAPS emotional working memory task will have greater DLPFC activation and greater dIPFC/sgACC anticorrelation than rTMS + cognitive SST (more robust)

Hypothesis 2c: rTMS + IAPS emotional task will have greater signal to noise (more selective).

Aim 3: to determine the effect of neuromodulation on DLPFC activation healthy participants will be randomized to one of the 3 task conditions: high-load cognitive SST, high-load IAPS task, or low-load SST (sham task condition). Following a 4 session course (2 session separated by at least 4 hours on one day, followed by 2 sessions separated by at least 4 hours on a second day) of either active rTMS or sham TMS neuromodulation in combination with the task condition participants will again have probe sessions in the scanner where DLPFC activation and connectivity will be determined. Following a 2-week interval, participants will receive the other stimulation condition (sham TMS if active first and active TMS if sham first).

[figure not shown]
Hypothesis 3a: Task (any of the 3) + active rTMS will result in greater DLPFC activation and greater dIPFC/sgACC anticorrelation than task plus sham rTMS

Hypothesis 3b: the IAPS task in combination with active rTMS will produce greater activation than the cognitive SST + active TMS or than control task + active TMS.

CONFIDENTIAL

4 Investigational Plan

Below is an example of the proposed study flow after screening visit. Please refer to attached task descriptions for further information:

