Significance: this protocol builds on the RDoC construct of cognitive control to assess the neural substrates involved in TMS activation as well as task-induced TMS augmentation. By using both a passive vs active version of the SST working memory task we can examine the effect of manipulation characteristics of tasks and by using cognitive vs. emotional versions of the task we can probe the contribution of emotional arousal to the effects. Further by randomizing subjects to one of three task conditions (including a task control condition) we can determine the effect of task augmentation on TMS.

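### The Aim 1 comparison of SST with IAPS cannot isolate an emotion effect, and the planned neutral and negative IAPS blocks, which could help, are assigned to no hypothesis or analysis

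*Combined protocol and SAP*

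**What the plan says.** Section 3.1 of the combined protocol and SAP sets two targets for Aim 1, an intensity effect and an emotion effect, both measured in the same participants. The comparison it then states is: "We will compare low-load vs. high-load brain activation and connectivity in the cognitive vs. emotional tasks". The Significance paragraph in Section 1.1 gives the reasoning: "by using cognitive vs. emotional versions of the task we can probe the contribution of emotional arousal to the effects". Section 4.1 labels the two tasks cognitive and emotion.

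The tasks differ in what is shown. The SST is "a cognitive task comparing low-load vs. high-load conditions in which the picture stimuli are letters". The IAPS task shows pictures at both loads, and "jittered within this design will be both neutral and negative blocks of IAPS pictures".

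Hypotheses 1a and 1b are load contrasts, each within one task. Hypothesis 1c is the emotion-related one: "The picture rating for arousal will be correlated with the activity in the DLPFC", and likewise with the connectivity measure. Later hypotheses compare the tasks directly: 2b predicts that "rTMS + the IAPS emotional working memory task will have greater DLPFC activation" than rTMS with the SST, and 3b that "the IAPS task in combination with active rTMS will produce greater activation than the cognitive SST + active TMS" or the control task.

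Section 8 contains a repeated measures ANOVA of change from baseline to post-stimulation for each task condition, and a comparison with published rates. It names no valence or arousal term.

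**The concern.** If emotion is inferred from the contrast between the tasks, it is tied to the change from letters to pictures. Two errors could follow. A difference that comes from the stimulus material could be reported as an emotion effect. Or a real emotion effect of the same size at low and high load could be missed, because a comparison of load effects removes it.

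The neutral and negative IAPS blocks hold the use of pictures constant while emotional content varies, so they are the natural control. The plan collects them but gives them no stated analytic role.

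**Working it through.** The plan gives no figure to reproduce. The check is what each reading of the stated comparison estimates.

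**Inputs from Section 3.1:** two tasks, each at two loads; letters in the SST and pictures in IAPS; neutral and negative blocks within IAPS.

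**Assumption:** half the IAPS blocks are negative at each load. The documents give no block counts and do not say whether valence is crossed with load.

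**Cells:** S = SST, N = IAPS neutral, G = IAPS negative, each at low (L) or high (H) load. Pooled over valence, I_L = (N_L + G_L)/2 and I_H = (N_H + G_H)/2.

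**Contrasts:**
- Load-by-task: (I_H − I_L) − (S_H − S_L)
- Overall task: (I_L + I_H)/2 − (S_L + S_H)/2
- Within IAPS: (G_L + G_H)/2 − (N_L + N_H)/2

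**Example.** An emotion effect of 1 at both loads adds 1 to G_L and G_H, so I_L and I_H each rise by 0.5. Load-by-task gives (0.5 − 0.5) − 0 = 0. Overall task gives (0.5 + 0.5)/2 − 0 = 0.5. Within IAPS gives (1 + 1)/2 − 0 = 1.

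The same arithmetic for each unit effect:

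| True effect of size 1 | Load-by-task | Overall task | Negative minus neutral |
|---|---|---|---|
| Letter-versus-picture offset, equal at both loads | 0 | 1 | 0 |
| Extra load effect specific to pictures | 1 | 0.5 | 0 |
| Emotion, equal at both loads | 0 | 0.5 | 1 |
| Emotion at high load only | 0.5 | 0.25 | 0.5 |

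**Sensitivity to the assumption.** In the overall task contrast, the weight on constant emotion equals the negative share: 0.33 to 0.67 if a third to two thirds of blocks are negative. The picture offset stays at 1. In load-by-task, the weight on constant emotion is the negative share at high load minus that at low load, so it is 0 whenever the shares are equal.

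**Estimability.** Take a model with intercept, load, picture, emotion, load-by-picture and load-by-emotion. With IAPS pooled over valence there are four cells and the rank is 4 of 6: emotion is aliased with picture, and load-by-emotion with load-by-picture. With IAPS split by valence and crossed with load there are six cells and the rank is 6 of 6. This needs no assumption about effect size, standard deviation or alpha.

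**Precision of the within-IAPS contrasts.** With equal, independent block noise of variance v per IAPS cell:
- Valence over both loads: 4 × 0.5² × v = v, relative standard error 1.
- Valence at one load: (1² + 1²) × v = 2v, relative standard error √2 = 1.41.
- Valence × load, (G_H − N_H) − (G_L − N_L): 4 × 1² × v = 4v, relative standard error 2.

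**The case against.** The strongest reply is that Hypothesis 1c is already the emotion test. The background in Section 1.1 contrasts magnitude of arousal with valence, so an arousal analysis is closer to the protocol's construct than a valence contrast, and the neutral and negative blocks may supply the range of arousal that 1c needs. Much of this stands. A reader might infer that Aim 1 has no emotion test at all, and the documents do not support that. They also give no reason to make negative minus neutral the sole definition. What remains is that 1c does not say whether the correlation runs over participants, blocks or pictures, gives no model, and is not tied to the emotion effect.

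A reader might also infer that the load comparison is contaminated by any difference between letters and pictures. It is not: a constant offset has weight 0 there. Confounding in that reading needs a load effect specific to pictures. The full offset enters only if the sentence is read as an overall task difference, which its low-versus-high wording does not clearly say.

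Nor do 2b and 3b claim an emotion effect. They are worded as comparisons of tasks. The risk lies in interpreting them through the rationale in Section 1.1.

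Two further limits apply. Section 4 refers to attached task descriptions that are not included here. They may give the rating source, block counts and crossing, so silence on these is not treated as a defect. And Section 8's failure to cover the task-only scan, which Section 6.2.1 describes as without a TMS probe, affects 1a and 1b equally; it is a general gap and not special to emotion.

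**Conclusion.** The point holds in this form. On either reading, the stated SST-versus-IAPS comparison cannot isolate emotion. Load-by-task gives a load-constant emotion effect weight 0 and a picture-specific load effect weight 1. The overall difference gives emotion 0.5 and the picture offset 1. The weights of 0 and 0.5 assume equal numbers of negative and neutral blocks at both loads; the aliasing when IAPS is pooled over valence does not depend on effect sizes or variances.

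Hypothesis 1c is a stated but underspecified arousal test, and the valence blocks have no stated analytic role. Because the emotion effect is part of the primary objective and the material to test it is already planned, this should be corrected before Aim 1 is analysed. It does not undermine 1a or 1b as tests of load within each task.

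**What to change.** In Sections 3.1 and 8, test the Aim 1 emotion effect within the IAPS task by two stated analyses:

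- **(a)** A negative-minus-neutral block contrast for DLPFC activation and for the connectivity measure, with valence × load if the two are crossed. If they are not crossed, run the contrast only at a load where both valences occur.
- **(b)** Hypothesis 1c as a within-participant analysis at picture or block level: one arousal slope per participant, then a test of the slopes across participants. State where the ratings come from. Both analyses are needed because negative minus neutral may mix valence with arousal.

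Keep 1a and 1b as the intensity effect. State that SST-versus-IAPS differences, including 2b and 3b, are task differences and will not be interpreted as evidence of an emotion effect.

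**Cost.** Only wording changes, with no new scans or participants, provided that block valence and per-picture or per-block ratings are recorded; the task descriptions may already cover this. The downside is precision. The valence main effect uses every IAPS block, but from block noise alone the standard error is about 1.4 times larger for valence at one load and 2 times larger for valence × load, with balanced blocks. For scale only, assuming a two-sided 5% test and 80% power, 25 participants would detect a negative-minus-neutral effect of about 0.58 SD of the paired difference, or 0.66 SD if 20 were evaluable. The plan states only the 25.

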Recent use of psychoactive medications, as determined by investigators
Otherwise determined by investigator to be unfit for participation:
ex) meets DSM criteria for current alcohol or substance use disorder (in last 3 months)

**Investigational
Product (drug,
biologic, device, etc.)**

**For Device include
the planned use**

MagVenture X100 Stimulator - *please refer to the 'Devices in Research Form' attached to this submission*

**For Drug, food,
cosmetic, etc.**

MagVenture Cool B65 Coil - *please refer to the 'Devices in Research Form' attached to this submission*

include the dose,

route of

administration and

dose regimen

MagVenture MRI B91 Coil - *please refer to the 'Devices in Research Form' attached to this submission*

CONFIDENTIAL

This material is the property of the University of Pennsylvania.

Duration of administration (if applicable)	The neuromodulation participants will receive is FDA-approved iTBS at 120% RMT stimulation intensity; triplet 50 Hz bursts, repeated at 5 Hz; 2 s on and 8 s off; 600 pulses per session; for a total duration of 3 min 9 s per session to the 'Fitzgerald Target' (identified via MRI imaging). Sham TMS will also be administered at the aforementioned parameters.
Reference therapy	When in the scanner, participants will receive single pulse TMS probes while completing tasks at 120% RMT with 77 total pulses.
Statistical Methodology	Efficacy within subjects: Repeated measures ANOVA will be used to assess changes from baseline to post-stimulation for each task condition. Efficacy between subjects: neuro-response rates and time to response will be compared with published rates within the literature to extrapolate the significance of this modality.
Safety Evaluations	No data or safety monitoring board will be necessary for this protocol. The principal investigator will be responsible for monitoring this protocol.
Data and Safety Monitoring Plan	No data or safety monitoring board will be necessary for this protocol. The principal investigator will be responsible for monitoring this protocol.

CONFIDENTIAL

This material is the property of the University of Pennsylvania.

BACKGROUND AND STUDY RATIONALE

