1.1 Background and Relevant Literature

The standard clinical technique for using repetitive transcranial magnetic stimulation (rTMS) for major depressive disorder (MDD) is associated with limited efficacy to date (Lefaucheur 2014; Berlim 2014). Among the potential causes of limited efficacy are the scalp based targeting technique that is currently the most common targeting method rather than techniques that incorporate fMRI-neuronavigation, which have been shown to have greater efficacy (Fitzgerald 2009a). Image guided TMS can target specific functional brain networks with greater resolution that takes into account individual differences in brain anatomy. Another technique for improving treatment efficacy may be to combine it with cognitive activation of the DLPFC designed to activate the same neural circuitry that is targeted by TMS. Cognitive paired associative stimulation builds on the well-established paradigm of paired associative stimulation (PAS). In that paradigm, co-activation of sensorimotor cortex with afferent stimulation of the median nerve timed to arrive as a TMS pulse is delivered to motor cortex, has been shown to increase cortical response to subsequent stimuli (Ziemann 2008). Analogously, simultaneous activation by 2 neurostimuli (TMS to DLPFC and task activating DLPFC) could result in greater cortical activation and have a greater effect on executive function cognitive control than either stimulus alone. Several studies now suggest that the brain "set" is critical in determining TMS effect (McKinley et al) and that simultaneous task activation can augment TMS efficacy (Li et al). It is not known whether the specific mode of cognitive activation is critical or whether the absolute amplitude of activation is more important. One theory proposes that tasks that activate the DLPFC promotion system via priming will maximally augment TMS treatment (Strauman 2013; Detloff & Strauman 2016), suggesting that the nature of the task is critical in TMS augmentation. Another set of observations (McTeague et al 2018) has found that magnitude but not the valence of emotional arousal predicted TMS augmentation. This suggests that it may not be task type but rather magnitude of emotional arousal that influences maximal TMS treatment augmentation.

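### The connectivity clauses of Hypotheses 2a and 2b include the tasks' own effect, and no planned contrast uses the task-alone runs to separate it from augmentation of TMS

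*Combined protocol and SAP*

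**What the plan says.** Section 3.1 sets Aim 2 as "to determine which task provides greater augmentation of the TMS-induced DLPFC activation". It lists three kinds of run: a task alone, rTMS with a task, and rTMS alone. Two directional hypotheses bear on this point. The first is "Hypothesis 2a: rTMS + either task will have greater DLPFC activation and greater dIPFC/sgACC anticorrelation than rTMS alone". The second, Hypothesis 2b, predicts that rTMS + IAPS exceeds rTMS + SST on the same two measures.

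The same section expects task conditions to go with these measures before any TMS is added:

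- Hypothesis 1a: "the high-load cognitive SST condition will produce greater DLPFC activation and dIPFC/sgACC anticorrelation" (relative to low load).
- Hypothesis 1b: "the high-load IAPS emotional pictures will produce higher activity in the DLPFC and dIPFC/sgACC anticorrelation" (relative to low load).
- Hypothesis 1c: "The picture rating for arousal will be correlated with the activity in the DLPFC and dIPFC/sgACC anticorrelation".

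Sections 3.1, 4.1 and 6 tie activation to a TMS probe and name connectivity beside it without such a tie. The Study Summary (reference therapy row) says "participants will receive single pulse TMS probes while completing tasks at 120% RMT with 77 total pulses". Section 8 offers a repeated measures ANOVA of change from baseline to post-stimulation for each task condition. It does not define baseline for Aim 2, and it names no between-task or task-by-TMS contrast.

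**The concern.** Whether a task augments TMS depends on what TMS adds with the task and what it adds without it. Hypothesis 2a holds TMS fixed and adds the task. Hypothesis 2b holds TMS fixed and swaps the task. Each difference includes the effect that the task would have had with the coil switched off. For connectivity, nothing in the plan removes that effect.

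The background in section 1.1 sets the standard that co-activation "could result in greater cortical activation and have a greater effect on executive function cognitive control than either stimulus alone". Hypothesis 2a tests against only one of those two stimuli. A task that shifts connectivity by itself can satisfy it while TMS does nothing.

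The risk is that a plain task effect is reported as augmentation of TMS. The error can also run the other way: if SST alone is the more anticorrelated task, 2b can miss a real advantage of IAPS. Aim 2 is secondary, but it is the trial's direct test of augmentation during stimulation.

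**Working it through.** **Inputs.** From the documents: n=25 (section 5.5), all runs within subject. The plan gives no alpha, effect size, SD, correlation or power for Aim 2, so there is no figure to reproduce. Assumed for illustration: two-sided 0.05; Fisher-z SD 0.25 (range 0.20 to 0.30); equal correlation r=0.5 between runs (range 0.3 to 0.7); task shifts of 0.05 to 0.15 in z. Significance is counted in the claimed direction only.

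**Step 1, what each contrast estimates.** Score connectivity so that larger means more anticorrelated. Let b be the level with no task and no TMS, T the TMS effect, K the task's own effect and A the augmentation (interaction).

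- TMS alone = b + T; task alone = b + K; TMS + task = b + T + K + A.
- 2a: (TMS + task) − TMS alone = K + A.
- 2b: (TMS + IAPS) − (TMS + SST) = (K_IAPS − K_SST) + (A_IAPS − A_SST).
- (TMS + task) − same task alone = T + A.
- Subtracted 2b: (TMS + IAPS − IAPS alone) − (TMS + SST − SST alone) = A_IAPS − A_SST.

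T does not appear in 2a, so 2a can be met with T = 0 and A = 0. Only the last contrast isolates a difference in augmentation.

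**Step 2, false claims in connectivity when A = 0.** The SD of a two-run difference is SD × √(2(1−r)) = 0.25 × √1 = 0.25. The noncentrality is shift × √25 / 0.25, with 24 df and a critical t of 2.064.

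| Task shift (z) | Noncentrality | Significant |
|---|---|---|
| 0.05 | 1.0 | 16% |
| 0.10 | 2.0 | 48% |
| 0.15 | 3.0 | 82% |

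For a 0.10 shift the range runs from 27% (SD 0.30, r=0.3) to 87% (SD 0.20, r=0.7). The figures apply to 2a with shift K, and to 2b with shift K_IAPS − K_SST. If the two tasks have equal effects alone, 2b keeps its nominal error rate.

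**Step 3, requiring both comparisons in 2a.** This was simulated with 40,000 trials, r=0.5, T = 0, A = 0 and task effects of 0.3, 0.5 and 0.8 SD (0.075, 0.125 and 0.20 in z at SD 0.25). Above TMS alone only: 30%, 67%, 97%. Above TMS alone and above the same task alone: 1.9%, 2.4%, 2.6%. If TMS has its own additive effect of 0.3 SD, the double requirement is met in 15%, 26% and 30%. Passing it therefore shows a joint effect, not one that is more than additive.

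**Step 4, power of the subtracted 2b.** The SD of the four-run contrast is SD × √(4(1−r)) = 0.25 × √2 = 0.354, twice the variance. For a true extra augmentation of 0.10 the noncentrality is 0.10 × 5 / 0.354 = 1.41 and power is 27%, against 48% for a two-run contrast of that size. If SST alone is more anticorrelated by 0.05, the stated 2b sees only 0.10 − 0.05 = 0.05 and its power is 16%; the subtracted contrast stays at 27%.

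**Step 5, where the task-alone and TMS-alone runs sit.** The Study Summary and section 3.1 put task alone inside the randomized order of Aim 2. Sections 4.1, 6 and 6.2.1 to 6.2.2 put it in a phase before the TMS runs. Section 6.2.3 lists three tasks with TMS and no TMS-alone run, while the Study Summary and sections 3.1, 4.1 and 6 list one.

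**The case against.** A reader might infer that all of 2a and 2b is confounded, activation included. The documents do not support that. Aim 2 speaks of TMS-induced activation, section 2 of TMS-evoked responses, and sections 3.1, 4.1 and 6 of activation to a probe; section 7.6 lists only single-pulse probes. If the pulse-evoked response is analysed with the task modelled apart, 2a and 2b compare the TMS response across task states and largely stand. What remains is that pulses fall during task performance and no model is written down. Only if total activation were analysed would the 30%, 67% and 97% of Step 3 carry over to 2a activation.

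A reader might also infer that the plan must show more-than-additive effects. Section 1.1 asks only for more than either stimulus alone, which additive effects can meet. Measured against that standard, 2a lacks one comparison, with task alone, and not a full interaction test.

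Three further points have force. Aim 2 names augmentation of activation only, and the connectivity clauses are valid as literal comparisons; harm arises when the result is called augmentation. Hypotheses 1a and 1b compare loads and 1c concerns arousal ratings, so none predicts a connectivity difference between IAPS and SST without TMS or gives the size of a task effect against no task. The ANOVA sentence in section 8 could be read as taking the task-alone scan for baseline, but it does not say so. The flow figure and attached task descriptions were not available to check.

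What stands is the connectivity point and the missing second comparison in 2a.

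**Conclusion.** The point holds for connectivity. As worded, 2a and 2b cannot separate task augmentation of TMS from the tasks' own effect on dlPFC/sgACC anticorrelation, and 2a can be met with no TMS effect. That follows from the algebra and needs no assumed value. The size does: with SD 0.25 and r=0.5, a task shift of 0.10 in z produces a significant 2a in 48% of trials without augmentation (27% to 87% over the ranges used). For 2b the same figures apply only if IAPS alone is the more anticorrelated task.

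Activation needs a defining sentence rather than a new contrast. This should be fixed before analysis; confidence is medium, because the outcome definitions are brief and the attachments are not visible.

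**What to change.** 1. State in sections 3.1 and 8 that Aim 2 activation is the pulse-evoked response with the task modelled separately. Hypotheses 2a and 2b can then keep their wording for activation.
2. For 2a connectivity, require for each task that TMS + task exceeds both TMS alone and the same task alone. Report this as a joint effect, not as more-than-additive augmentation; an interaction test would need a no-task, no-TMS reference, which the documents do not name as a condition.
3. For 2b connectivity, keep the stated contrast and add (TMS + IAPS − IAPS alone) against (TMS + SST − SST alone), with the same load in both runs of a pair. Claim that IAPS augments more only if the subtracted contrast supports it.
4. Reconcile the sections on whether task alone is inside the randomized order or at an earlier scan, and on whether a TMS-alone run takes place. Without that run 2a has no comparator.

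The cost is mostly text. Task-alone runs for both tasks are already scheduled, so the 2b addition needs no new scan; 2a needs the TMS-alone run that most sections list. The subtracted contrast doubles the variance (Step 4), so a null result would say little. If the task-alone runs are at an earlier visit, a session effect common to both tasks cancels in 2b but not in the 2a comparison with task alone. Task-specific learning would not cancel in either, which is why the subtracted contrast belongs beside the stated one and does not replace it.
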